	
• Biopsy was collected \leq 6 months before 1st dose of study treatment and available at the site.• No antineoplastic therapy was given to the patient since collection of biopsy (with the exception of IO pretreated cutaneous melanoma, HNSCC and RCC).• Part 1 – 3 only: Patients (other than those with DLBCL) must previously have received at least 1 and no more than 3 prior lines of therapy (with the exception of IO pretreated cutaneous melanoma, HNSCC and RCC) for their disease, specifically including the following, unless considered inappropriate for the patient (e.g. safety concern, label contraindication):• MSS CRC:
• Patients with MSS colorectal cancer must have received (or be intolerant to) prior therapy with fluoropyrimidine-oxaliplatin- and irinotecan- based regimens.• Patient with wild type RAS must have received prior treatment with an antibody targeting EGFR (e.g. cetuximab or panitumumab)• TNBC:
• Part 1: Patients with triple negative breast cancer must have received a prior taxane containing regimen.• Part 3:
• Patients should have documented disease progression following, or intolerance to, no more than 2 prior lines of chemotherapy for advanced or metastatic disease. Neoadjuvant and/or adjuvant chemotherapy administered with curative intent will count as one prior line of therapy, if disease recurred within 12 months of the last treatment.• Patients must have received prior systemic treatment that included taxane-based chemotherapy for (neo) adjuvant or metastatic disease.• Patients should have a known PD-L1 status as per local available testing determined by VENTANA PD-L1 SP142 Assay with IC score of 0 (<1%)• Urothelial Cancer:
• Patients with urothelial cancer must have received a prior platinum-containing regimen or be ineligible for cisplatin.• RCC:
• IO naive RCC: Patients with renal cell carcinoma must have received a prior VEGF tyrosine kinase inhibitor (TKI).• IO pretreated RCC: Patients with RCC with no more than 2 prior lines of therapy. Patient must have received a prior VEGF TKI and have been pretreated with an anti-PD-1/PD-L1 as a single agent or in combinations• HNSCC:
• IO Naive HNSCC: Patients with squamous cell carcinoma of head and neck (HNSCC) with no more than 3 prior lines of therapy. Patient must have received a prior platinum-containing regimen and have not been previously treated with any anti-PD1/L1 agents in single agent/combinations.• IO pre-treated HNSCC: Patients with HNSCC with no more than 2 prior lines of therapy. Patient must have received a prior platinum-containing regimen and have been pretreated with an anti-PD-1/PD-L1 as a single agent or in combinations• Cutaneous Melanoma:
• Patients must previously have received at least 1 and no more than 2 prior lines of therapy.

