4.1 Description of study design

[figure not shown]
This is an open-label multi-part, phase II study evaluating the combination of NIR178 and PDR001 in patients with advanced solid tumors and diffuse large B cell lymphoma (DLBCL). Patients will receive treatment with the combination until disease progression (assessed by investigator per iRECIST ([Appendix 3](#)) or [Cheson et al \(2014\)](#) for DLBCL), unacceptable toxicity, start of a new anti-neoplastic therapy, or discontinuation at the discretion of the investigator or patient, lost to follow-up, death or study is terminated by the sponsor. All patients who discontinue from study treatment due to disease progression must have their progression clearly documented. All disease assessments will be performed locally by the investigator.

Submission of a pre-treatment and on-study tumor sample is mandated for all patients enrolled. The timing of the sample collection will be: 1) A pre-treatment biopsy (defined as obtained after most recent therapy and within 6 months preceding first dose of study treatment) 2) on-treatment tumor biopsy taken on C2D15 (+15 days). Exceptions may be made on a case by case basis after discussion between Novartis and the Investigator. An optional biopsy may be collected at end of treatment and at disease progression when patients continue on study treatment due to overall clinical benefit.

This phase II study has 3 parts ([Figure 4-1](#)). Parts 1 and 2 will enroll in parallel, and Part 3 will open once results from Parts 1 and 2 are available. As of protocol amendment 6, Part 3 will be opened in parallel with Part 1, using the NIR178 continuous dosing schedule, which was identified as the preferred dosing schedule in Part 2 of the study.

[figure not shown]
- Part 1: Multi-arm Bayesian adaptive signal finding design in 13 groups (some of which in subgroups based on mutation status or prior treatment), and diffuse large B cell lymphoma (DLBCL) with continuous dosing of NIR178 in combination with PDR001.
- Part 2: Exploration of continuous and intermittent NIR178 schedules in combination with PDR001 in patients with advanced non-small cell lung cancer (NSCLC).

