5.2 Inclusion criteria

Patients eligible for inclusion in this study have to meet **all** of the following criteria:

1. Male or female patients ≥ 18 years of age.
For Japan only: written consent is necessary both from the patient and his/her legal representative if he/she is under the age of 20 years.
2. Histologically documented advanced or metastatic solid tumors or lymphomas
 - a. **Part 1:** histologically confirmed renal cell carcinoma (RCC), pancreatic cancer, urothelial cancer, head and neck squamous cell carcinoma (HNSCC), diffuse large B-cell lymphoma (DLBCL), microsatellite stable colorectal cancer (MSS CRC), triple negative breast cancer (TNBC), cutaneous melanoma or mCRPC
 - Patients with colorectal cancer must have microsatellite stable (MSS) disease as detected by PCR-based assay or loss of mismatch repair (MMR) protein expression by immunohistochemistry and confirmed RAS genotype by standard testing of tumor specimen based on local available laboratory data.
 - Patients with unresectable or metastatic cutaneous melanoma that have confirmed BRAF V600E status by standard testing of tumor specimen by local available laboratory data.
 - b. **Part 2:** histologically confirmed diagnosis of advanced/metastatic NSCLC. For those with mixed histology, there must be a predominant histology
 - Patients should have confirmed EGFR and ALK genotype when clinically indicated and performed per standard testing of tumor specimen based on local laboratory data.
 - c. **Part 3:** histologically confirmed diagnosis of selected advanced/metastatic malignancies should Part 3 be opened to enrollment. As of protocol amendment 6, Part 3 will open and enroll TNBC patients with PD-L1 SP-142 IC=0. A second tumor group may be considered for Part 3 following analysis of data from Part 1.
 - d. **Safety run-in** part in Japanese patients can enroll any tumor type included in Parts 1, 2 and 3.
3. Patient (except for those participating in Japanese safety run-in) must have a site of disease amenable to biopsy, and be a candidate for tumor biopsy according to the treating institution's guidelines. Patient must be willing to undergo a new tumor biopsy at screening, and again during therapy on this study. The use of a recent sample is permitted under the following conditions (both must be met):
 - a. Biopsy was collected ≤ 6 months before 1st dose of study treatment
 - b. No immunotherapy was given to the patient since collection of biopsy.

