5.3 Exclusion criteria

Patients eligible for this study must not meet **any** of the following criteria:

1. Symptomatic or uncontrolled brain metastases requiring concurrent treatment, inclusive of but not limited to surgery, radiation and/or corticosteroids.
2. History of another primary malignancy except for:
 - Malignancy treated with curative intent and with no known active disease ≥ 2 years before the first dose of study drug and of low potential risk for recurrence
 - Adequately treated non-melanoma skin cancer or lentigo maligna without evidence of disease
 - Adequately treated carcinoma in situ without evidence of disease
3. Active or prior documented autoimmune disease within the past 2 years
NOTE: Patients with vitiligo, Grave's disease, or psoriasis not requiring systemic treatment (within the past 2 years) are not excluded.
4. Active or prior documented inflammatory bowel disease (e.g., Crohn's disease, ulcerative colitis)
5. History of interstitial lung disease or non-infectious pneumonitis
6. History of primary immunodeficiency
7. History of allogeneic organ or stem cell transplant
8. Ongoing or prior treatment with A2aR inhibitors. Patients previously treated with A2aR inhibitors for non-oncologic indications (e.g. Parkinson's disease) may be considered for enrollment on a case by case basis.
9. More than 2 or 3 prior lines of therapy (as indicated for each tumor type in the inclusion criteria 4), except for Japanese safety run-in part and DLBCL patients.
10. Systemic anti-cancer therapy within 2 weeks of the first dose of study treatment.
For cytotoxic agents that have major delayed toxicity, e.g. mitomycin C and nitrosoureas, 6 weeks is indicated as washout period. For patients receiving anticancer immunotherapies, 4 weeks is indicated as the washout period. GnRH therapy to maintain effective testosterone suppression levels is allowed for mCRPC patients.

11. Non-palliative radiotherapy within 2 weeks prior to the first dose of study drug. Palliative radiotherapy to a limited field, such as for the treatment of bone pain or a focally painful tumor mass is allowed. To allow for assessment of response to treatment, patients must have remaining measurable disease that has not been irradiated.
12. Major surgery within 2 weeks of the first dose of study treatment (mediastinoscopy, insertion of a central venous access device, and insertion of a feeding tube are not considered major surgery).

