7.1.1 Screening

The IRB/IEC study approved informed consent form (ICF) must be signed and dated before any study-specific screening procedure is performed. Procedures which are part of the clinical routine during the initial diagnostic work-up of the patient may be obtained before obtaining the ICF. A copy of the ICF must be given to the patient or to the person signing the form. The investigator or designee must record the date when the study informed consent was signed in the medical records of the patient.

Patients will be evaluated against study inclusion and exclusion criteria and safety assessments. For details of assessments, refer to [Table 7-1](#), [Table 7-2](#) and [Table 7-3](#). Screening assessments must be completed within 21 days prior to the first dose of treatment except for the radiological tumor assessment which should be performed within 28 days prior to the first dose. Screening assessments must be repeated if outside of screening windows. Patients are allowed to re-screen after abnormal labs or symptoms are corrected or treated.

Submission of a newly obtained tumor sample (formalin fixed, in ethanol) is required from all patients (except for patients in Japanese safety run-in part) at screening, unless the patient has a recently obtained tumor sample that meets the following criteria (both criteria must be met):

- Biopsy sample was collected \leq 6 months before 1st dose of study medication and the sample is available at the site.
- No immunotherapy was given to the patient since collection of biopsy sample.

For details refer to [Section 7.2.4](#).

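### The protocol states three different conditions for an archival baseline biopsy, so the secondary TIL/CD8 change from baseline can include the effect of a therapy given between biopsy and first dose

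*Protocol*

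**What the plan says.** A new tumor biopsy at screening is the default. A recent sample may be used instead, and all versions of the rule share the same age limit: "Biopsy was collected ≤ 6 months before 1st dose of study treatment". They differ on what treatment may have been given in between.

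- Protocol 5.2, criterion 3b: "No immunotherapy was given to the patient since collection of biopsy". Protocol 7.1.1 repeats this: "No immunotherapy was given to the patient since collection of biopsy sample". Neither exempts any group.
- Protocol summary, inclusion criteria: "No antineoplastic therapy was given to the patient since collection of biopsy (with the exception of IO pretreated cutaneous melanoma, HNSCC and RCC".
- Protocol 4.1: "A pre-treatment biopsy (defined as obtained after most recent therapy and within 6 months preceding first dose of study treatment". No group is exempt, but the paragraph goes on: "Exceptions may be made on a case by case basis after discussion between Novartis and the Investigator".

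All four statements are current text; none comes from an amendment log. Patients in the Japanese safety run-in are exempt from the biopsy requirement.

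The sample serves as baseline for a secondary endpoint in Table 3-1, the change from baseline in tumor-infiltrating lymphocytes such as CD8 by immunohistochemistry. In the public text, Protocol 10.5.3.2 limits change-from-baseline analyses to patients with measurable samples before and after treatment. It sets no condition on therapy given between the baseline sample and first dose.

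**The concern.** A pre/post change in CD8 infiltrate is read as the effect of NIR178 plus PDR001. That reading needs a baseline that shows the tumor as it was when study treatment began. SAP 2.1.1.4 defines baseline in that spirit, as the patient's state before study treatment starts. If chemotherapy, a TKI or an anti-PD-(L)1 course falls between the sample and first dose, the measured change contains that therapy's effect as well, and the pair alone cannot separate the two.

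There is also an eligibility question. The archival condition is part of an inclusion criterion, and Protocol Section 12 allows no authorised deviations. Whether the same patient complies or deviates depends on which section the site follows.

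**Working it through.** The plan gives no figure to reproduce, so the check has two steps.

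**Step 1. Apply each rule to the same patients.** Take an archival sample within the 6-month limit and ask whether it is accepted. For 4.1 the entry is the general rule, before any case-by-case exception.

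| Patient group | Therapy after the biopsy | 5.2 (3b) and 7.1.1 | Protocol summary | 4.1 |
|---|---|---|---|---|
| Not IO-pretreated | Chemotherapy or TKI | Accept | Refuse | Refuse |
| Not IO-pretreated | Anti-PD-(L)1 | Refuse | Refuse | Refuse |
| IO-pretreated melanoma, HNSCC, RCC | Chemotherapy or TKI | Accept | Accept | Refuse |
| IO-pretreated melanoma, HNSCC, RCC | Anti-PD-(L)1 | Refuse | Accept | Refuse |

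The four statements therefore reduce to three rules. The 5.2/7.1.1 rule and the summary rule conflict in both directions: row 1 passes only the former, row 4 only the latter. Section 4.1 is stricter than both.

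**Step 2. How much therapy could fit in the gap.** Inputs: the 6-month limit above, and the washouts in exclusion criterion 10. These are "Systemic anti-cancer therapy within 2 weeks of the first dose of study treatment"; "For patients receiving anticancer immunotherapies, 4 weeks is indicated as the washout period"; and 6 weeks for cytotoxics with major delayed toxicity.

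- 6 months in weeks: (365.25 / 12) × 6 / 7 = 26.1.
- Room = 26.1 weeks minus the washout:
  - systemic therapy in general: 26.1 − 2 = 24.1 weeks;
  - anti-PD-(L)1: 26.1 − 4 = 22.1 weeks;
  - cytotoxics with major delayed toxicity: 26.1 − 6 = 20.1 weeks.

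A course that fits within about 20 to 24 weeks could lie wholly between the baseline sample and first dose. The documents give neither the length of prior lines nor the share of archival samples, so no frequency follows from this.

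**The case against.** Several points on the other side stand.

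- **A site can satisfy every version at once.** Any sample that meets 4.1 also meets 5.2, 7.1.1 and the summary. The statements are inconsistent, but compliance with all of them is possible.
- **Section 4.1 has its own exceptions.** They soften its refusals, although an unspecified exception does not say which general rule applies.
- **Relevant text is withheld.** Section 7.1.1 refers to Protocol 7.2.4 for details, and the SAP change log cites SAP 2.6.7 on tumor immune infiltrate. Neither is in the public documents. Either may already define acceptable pairs, so neither can be called deficient.
- **The endpoint is secondary.** Protocol 10.5.3.1 says the data will only be listed if samples are too few. ORR, the futility rule and the success rule do not use it.

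Four stronger readings are tempting, and the documents do not support them.

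- A reader might infer that a baseline before anti-PD-1 therapy is generally allowed. Only the summary's exemption allows it. Sections 5.2, 7.1.1 and 4.1 all refuse it, and Section 5.1 ties enrollment to the listed criteria.
- A reader might attach a percentage. Assuming 20–50% archival samples, half of them with intervening therapy, gives 0.20 × 0.5 = 10% to 0.50 × 0.5 = 25% of pairs. Neither input is in the documents, so the figure is not evidence.
- A reader might infer confounded comparisons between tumor types. No such TIL comparison is visible. The visible comparison of immune modulation is across the randomized Part 2 schedules within NSCLC (Protocol 4.1.2).
- A reader might infer that the case for the higher NIR178 dose in Protocol 2.3 is undermined. CD8 data are one of several supports there, and nothing shows that those pairs had intervening therapy.

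**Conclusion.** The inconsistency is real and lies in current text. The operative criterion (5.2, with 7.1.1) accepts an archival sample followed by chemotherapy or a TKI, which 4.1 and the summary refuse. The summary alone accepts one followed by anti-PD-(L)1 in the IO-pretreated groups. Either way the secondary TIL/CD8 change from baseline can include another therapy's effect, and the visible analysis text has no filter for it.

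The size is bounded only in time, at about 20 to 24 weeks of possible intervening therapy. The number of affected pairs, and the direction and amount of any bias, cannot be computed from the documents. The point applies only where an archival sample replaced the screening biopsy. It assumes that at least some such samples had therapy in between, and that the withheld sections do not already remove those pairs. If they do, only the wording conflict remains.

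**What to change.** **Protocol.** Bring the summary, 4.1, 5.2 criterion 3b and 7.1.1 to one rule consistent with the 4.1 definition, that is, a sample taken after the last therapy. State how two treatments permitted by exclusion criteria 10 and 11 count under that rule: maintenance GnRH therapy in mCRPC and limited-field palliative radiotherapy. A blanket ban on all antineoplastic therapy since the biopsy could otherwise disqualify an archival sample from an mCRPC patient on continuous GnRH therapy.

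**Analysis.** Unless SAP 2.6.7 or Protocol 7.2.4 already does so, compare each baseline biopsy date with the dates on the Prior Antineoplastic Therapy eCRF (Protocol 6.3). Summarise the change in immune infiltrate without pairs that have intervening therapy, and list those pairs separately with the type of therapy. Use recorded dates and flag partial ones, because the prior-therapy imputation in SAP 5.1.3.1 can move a date close to the start of study treatment and so create an apparent overlap.

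**Cost.** Wording in four places and one date comparison on data already collected, with no added procedure. A few pairs leave the TIL summary. SAP Section 4 says the study is closed out for lack of sufficient efficacy, so rewording can no longer change which samples were taken. The date check is the part that still matters.

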7. *(In protocol amendment 4, this inclusion criteria has been incorporated as part of inclusion criteria #4.)* For patients with NSCLC, EGFR mutation with exon 19 deletion or L858R mutation (Exon 21) or anaplastic lymphoma receptor tyrosine kinase (ALK) rearrangement positive must have failed prior Tyrosine-kinase inhibitor (TKI) therapy.

8. Patients must have measurable disease, defined as at least one lesion that can be accurately measured in at least one dimension (longest diameter to be recorded for non-nodal lesions and short axis for nodal lesions) as >20 mm with conventional techniques or as >10 mm with spiral computer tomography (CT) scan, Magnetic Resonance Imaging (MRI), or calipers by clinical exam.
Note: If prior treatment was discontinued due to toxicity, patient must have continued evidence of measurable or evaluable disease.
9. Patient has an Eastern Cooperative Oncology Group (ECOG) performance status 0-2.
10. Written informed consent must be obtained prior to any screening procedures. If consent cannot be expressed in writing, it must be formally documented and witnessed, ideally via an independent trusted witness.

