14.2.3 Definitions

14.2.4 Disease measurability

In order to evaluate tumors throughout a study, definitions of measurability are required in order to classify lesions appropriately at baseline. In defining measurability, a distinction also needs to be made between nodal lesions (pathological lymph nodes) and non-nodal lesions.

- **Measurable disease** - the presence of at least one measurable nodal or non-nodal lesion. If the measurable disease is restricted to a solitary lesion, its neoplastic nature should be confirmed by cytology/histology.

For patients without measurable disease see [Section 14.2.26](#).

Measurable lesions (both nodal and non-nodal)

- **Measurable non-nodal** - As a rule of thumb, the minimum size of a measurable non-nodal target lesion at baseline should be no less than double the slice thickness or 10mm whichever is greater - e.g. the minimum non-nodal lesion size for CT/MRI with 5mm cuts will be 10 mm, for 8 mm contiguous cuts the minimum size will be 16 mm.
- **Lytic bone lesions or mixed lytic-blastic lesions with identifiable soft tissue components** that can be evaluated by CT/MRI, can be considered as measurable lesions, if the soft tissue component meets the definition of measurability.
- **Measurable nodal lesions (i.e. lymph nodes)** - Lymph nodes ≥ 15 mm in short axis can be considered for selection as target lesions. Lymph nodes measuring ≥ 10 mm and < 15 mm are considered non-measurable. Lymph nodes smaller than 10 mm in short axis at baseline, regardless of the slice thickness, are normal and not considered indicative of disease.

- **Cystic lesions:**
 - Lesions that meet the criteria for radiographically defined simple cysts (i.e., spherical structure with a thin, non-irregular, non-nodular and non-enhancing wall, no septations, and low CT density [water-like] content) should not be considered as malignant lesions (neither measurable nor non-measurable) since they are, by definition, simple cysts.
 - ‘Cystic lesions’ thought to represent cystic metastases can be considered as measurable lesions, if they meet the definition of measurability described above. However, if noncystic lesions are present in the same patient, these are preferred for selection as target lesions.

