- Non-measurable lesions - all other lesions are considered non-measurable, including small lesions (e.g. longest diameter <10 mm with CT/MRI or pathological lymph nodes with ≥ 10 to < 15 mm short axis), as well as truly non-measurable lesions e.g., blastic bone lesions, leptomeningeal disease, ascites, pleural/pericardial effusion, inflammatory breast disease, lymphangitis cutis/pulmonis, abdominal masses/abdominal organomegaly identified by physical exam that is not measurable by reproducible imaging techniques.

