14.2.5 Eligibility based on measurable disease

If no measurable lesions are identified at baseline, the patient may be allowed to enter the study in some situations (e.g. in Phase III studies where PFS is the primary endpoint). However, it is recommended that patients be excluded from trials where the main focus is on the Overall Response Rate (ORR). Guidance on how patients with just non-measurable disease at baseline will be evaluated for response and also handled in the statistical analyses is given in [Section 14.2.26](#).

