14.2.26 Handling of patients with non-measurable disease only at baseline

It is possible that patients with only non-measurable disease present at baseline are entered into the study, either because of a protocol violation or by design (e.g. in Phase III studies with PFS as the primary endpoint). In such cases the handling of the response data requires special consideration with respect to inclusion in any analysis of endpoints based on the overall response evaluations.

It is recommended that any patients with only non-measurable disease at baseline should be included in the main (ITT) analysis of each of these endpoints.

Although the text of the definitions described in the previous sections primarily relates to patients with measurable disease at baseline, patients without measurable disease should also be incorporated in an appropriate manner. The overall response for patients with measurable disease is derived slightly differently according to [Table 14-6](#).

Table 14-6 Overall lesion response at each assessment: patients with non-target disease only

Non-target lesions	New Lesions	Overall lesion response
CR	No	CR
Non-CR/Non-PD ¹	No	Non-CR/non-PD
UNK	No	UNK
PD	Yes or No	PD
Any	Yes	PD

¹ As defined in [Section 14.2.8](#).

In general, the **non-CR/non-PD response** for these patients is considered equivalent to an SD response in endpoint determination. In summary tables for best overall response patients with only non-measurable disease may be highlighted in an appropriate fashion e.g. in particular by displaying the specific numbers with the non-CR/non-PD category.

In considering how to incorporate data from these patients into the analysis the importance to each endpoint of being able to identify a PR and/or to determine the occurrence and timing of progression needs to be taken into account.

For ORR it is recommended that the main (ITT) analysis includes data from patients with only non-measurable disease at baseline, handling patients with a best response of CR as “responders” with respect to ORR and all other patients as “non-responders”.

For PFS, it is again recommended that the main ITT analyses on these endpoints include all patients with only non-measurable disease at baseline, with possible sensitivity analyses which exclude these particular patients. Endpoints such as PFS which are reliant on the determination and/or timing of progression can incorporate data from patients with only non-measurable disease.

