14.5 Appendix 5: Efficacy guideline for prostate cancer (based on PCWG3)

The predominant manifestations of progression of prostate cancers are rising prostate-specific antigen (PSA) values, new lesions on bone scan, new symptoms of disease, and an increase in a measurable tumor mass. Biochemical failure as represented by rising PSA is generally the first indication of recurring disease. Moreover, the prostate Cancer Clinical Trials Working Group emphasizes the importance of keeping patients on trial until radiographic or symptomatic progression, which better reflects a change in clinical status, is documented and that an effort is made not to discontinue therapy solely on the basis of a rise in PSA in the absence of other indicators of disease progression. This is particularly relevant for patients with low PSA values at entry and those with a slow rate of rise in PSA at progression (Scher et al 2016). Please refer to Table 14-19 for assessments and progression criteria on the basis of changes in PSA, bone metastases, and measurable disease (Scher et al 2016).

Table 14-20 PCWG3 criteria of progression by disease manifestation

Assessment	Evaluation Criteria for disease progression
PSA	Obtain sequence of rising values at a minimum of 1-week intervals 1 ng/mL minimum starting value if confirmed rise is only indication of progression unless pure small-cell carcinoma Estimate pre-therapy PSA-DT if 3 or more values available 4 or more weeks apart
Target lesions	Nodal or visceral progression sufficient for trial entry independent of PSA Measurable lesions not required for entry Use RECIST (v1.1) to record soft-tissue (nodal and visceral) lesions as target or non-target Previously normal (< 1.0-cm) lymph nodes must have grown by ≥ 5 mm in the short axis from baseline or nadir and be ≥ 1.0 cm in the short axis to be considered to have progressed. If the node progresses to ≥ 1.5 cm in the short axis, it is measurable; nodes that have progressed to 1.0 to less than 1.5 cm are pathologic, subject to clinical discretion, and nonmeasurable. For existing pathologic adenopathy, progression is defined per RECIST 1.1 Record presence of nodal and/or visceral disease separately
Prostate	Record prior treatment of primary tumor Perform directed pelvic imaging (CT, MRI, PET/CT, endorectal MRI, transrectal ultrasound) to document presence or absence of disease

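### Inclusion criterion 8 accepts nodes and small lesions that Appendix 2 calls non-measurable, so some eligible patients would have their primary ORR scored by a different response rule

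*Protocol*

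**What the plan says.** **Eligibility.** Protocol Section 5.2, criterion 8, and the Protocol summary require at least one measurable lesion. It is judged by longest diameter for non-nodal lesions and by "short axis for nodal lesions) as >20 mm with conventional techniques or as >10 mm with spiral computer tomography (CT) scan"; the 10 mm limit extends to MRI and calipers. Nodes have no separate cut-off.

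**Scoring.** Protocol Section 10.4.1 and SAP Section 2.5.1 score solid tumors by RECIST 1.1 as set out in Protocol Appendix 2. Section 14.2.4 of that appendix sets a 15 mm minimum for nodes: those that size or larger "mm in short axis can be considered for selection as target lesions", while "Lymph nodes measuring ≥ 10 mm and < 15 mm are considered non-measurable". The list of non-measurable lesions repeats this. A non-nodal target must reach the greater of 10 mm and twice the slice thickness; the appendix's own example is 16 mm with 8 mm cuts. Appendix 3 (iRECIST) also uses 15 mm for nodal lesions.

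**Patients without a measurable lesion.** Section 14.2.5 says that "it is recommended that patients be excluded from trials where the main focus is on the Overall Response Rate (ORR"). If they do enter, Section 14.2.26 states: "For ORR it is recommended that the main (ITT) analysis includes data from patients with only non-measurable disease at baseline". Best response CR makes the patient a responder and anything else a non-responder. Table 14-6 offers CR, non-CR/non-PD, UNK and PD.

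**Denominator.** ORR is primary in all three parts. It is taken over all treated patients in Parts 1 and 3 and all randomized patients in Part 2 (Protocol Section 10.1.1).

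**The concern.** The rule that admits patients and the rule that scores them use the same term for different things. Criterion 8 exists to make sure that response can be assessed; exclusion criterion 11 gives that reason when it asks for remaining unirradiated measurable disease. As written, criterion 8 lets in patients in whom the usual form of response, a 30% fall in the sum of diameters, cannot be recorded.

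At stake is the meaning of the primary endpoint in small groups. Part 1 groups are generally capped at 30 patients and the Part 3 TNBC group is 20 to 30. The Part 1 decision compares ORR with fixed limits C1 and C2 (Protocol Table 10-1, SAP Table 2-4), and Part 3 reports posterior probabilities for fixed ORR intervals. If a few patients per group respond by another rule, the comparison is no longer like with like.

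**Working it through.** **1. The two definitions side by side**

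| Lesion | Criterion 8 (CT/MRI) | Appendix 2, Section 14.2.4 | Gap |
|---|---|---|---|
| Node, short axis | >10 mm | at least 15 mm | >10 to <15 mm |
| Non-nodal, 5 mm cuts | >10 mm | max(10, 2 × 5) = 10 mm | none |
| Non-nodal, 8 mm cuts | >10 mm | max(10, 2 × 8) = 16 mm | >10 to <16 mm |

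Section 14.2.6 prefers 5 mm cuts and allows up to 8 mm. The nodal gap is always present. The non-nodal gap opens only above 5 mm.

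**2. What happens to a patient in the gap.** With no target lesion, Table 14-6 applies and PR is not available. The only route to response is CR. Under Section 14.2.13 a non-target node is CR once its short axis is below 10 mm, and a non-nodal lesion must disappear.

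**3. Sole node of d mm.** CR requires shrinkage of just over 1 − 10/d. PR for a target lesion requires 30%.

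| d (mm) | Shrinkage for CR |
|---|---|
| 11 | 1 − 10/11 = 9% |
| 12 | 1 − 10/12 = 17% |
| 13 | 1 − 10/13 = 23% |
| 14 | 1 − 10/14 = 29% |
| 14.9 | 1 − 10/14.9 = 33% |

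The two are equal at d = 10/0.7 = 14.29 mm. Below that, the patient in the gap becomes a responder with less shrinkage than a patient with a target lesion needs.

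**4. Cases where response is harder.** A sole 11 mm lung nodule on 8 mm cuts must vanish (100%, against 30% if it were a target). With several lesions, each must resolve. Take nodes of 12 and 14 mm (sum 26) that shrink to 7 and 11 mm (sum 18). The sum falls by (26 − 18)/26 = 31%, enough for PR had they been targets, but one node is still at least 10 mm, so there is no CR and no response.

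**5. Net effect.** Let p be the ORR in patients with a target lesion, f the share without one, and c their CR rate. Then

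expected ORR = p(1 − f) + f·c, and the shift is f(c − p).

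The sign is that of c − p. Steps 3 and 4 show that c can lie on either side of p. The documents give neither f nor c.

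**6. How much one patient matters (Part 3).** The plan's figure first: with prior Beta(0.176, 1) and 3/20 responders, the posterior is Beta(3.176, 18) and P(ORR ≥ 13%) = 54.8%, as in Protocol Table 10-7. Now assume, for illustration only, that one of the 20 had no target lesion.

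- If that patient was a non-responder, the ORR among patients with a target lesion is 3/19: Beta(3.176, 17) gives 58.3%.
- If that patient was one of the three responders, it is 2/19: Beta(2.176, 18) gives 31.3%.

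A single such patient can move the headline probability up by 3.5 points or down by 23.5 points.

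**The case against.** The strongest reply is that the plan already foresees these patients. Section 14.2.26 keeps them in the main analysis with a defined responder rule, and this review would also keep that analysis as primary. Few may exist: the patient must have no other measurable lesion, must have advanced disease with a site that can be biopsied, and must have had a lesion judged accurately measurable. The slice-thickness rule is described as a rule of thumb, and 5 mm cuts are preferred. The study is also being closed out for lack of sufficient efficacy (SAP Section 4), so rewriting eligibility changes nothing for those enrolled.

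Much of this stands, and it limits the weight of the point. It does not remove the contradiction. A handling rule for patients who slip in is not a reason for the entry criterion to admit them, and Section 14.2.5 advises against it in a trial of this kind. SAP Section 2.5.1 defers to Appendix 2 and Section 2.5.4 lists no sensitivity analysis. The public text shows no ORR restricted to patients with a target lesion, although the subsection after 2.5.4 is blacked out.

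A reader might go further and infer that these patients are bound to be non-responders, so that ORR is diluted and power lost. The documents do not support that: CR counts as a response, and step 3 shows that it can be the easier target. A power loss could be computed only by assuming both the share affected and a CR rate of zero. A reader might also expect particular tumor groups to be hit hardest, but the documents say nothing on how often disease is nodal only in any group.

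**Conclusion.** The inconsistency is real and present in the current text. Criterion 8 and the Protocol summary define measurable disease more loosely than the appendix that scores the primary endpoint. Some eligible RECIST-assessed patients would therefore have no target lesion, no PR category, and a response defined on a different scale from C1 and C2. DLBCL is not affected, because it is scored by Cheson.

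The direction of any bias cannot be determined from the documents, and its size is unknown because the number of such patients is not reported. It is zero if there are none. The Part 3 figures rest on an assumed single patient and show sensitivity only; they do not estimate what happened. With enrollment over, the reporting step is the part that still matters.

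**What to change.** **Protocol.** Reconcile criterion 8 in Section 5.2 and the same text in the Protocol summary with Sections 14.2.4 and 14.2.5, so that for RECIST-assessed tumors eligibility uses the Appendix 2 definition of a measurable lesion.

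**SAP, before database lock.**

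- Report, per group, the number of patients with no baseline target lesion. Count nodes by recorded short axis against the 15 mm limit as well as by the site's target label, since criterion 8 may have led a site to record a smaller node as a target.
- Keep the full-analysis-set ORR as primary.
- Add a supportive ORR in full-analysis-set patients with at least one RECIST 1.1 target lesion, leaving out DLBCL.
- Rerun the Part 1 positivity rule in that subset only if the count is not zero.

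**Cost.** Slightly narrower eligibility for any future enrollment, a smaller supportive denominator, and possibly one extra run of the hierarchical model. Target lesions are already numbered and measured on the eCRF, so no new data are needed for the count. If the count is zero, the matter closes with one sentence in the study report.
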